7 STUDY MEDICATION (STUDY DEVICE OR OTHER STUDY INTERVENTION)

7.1 Description

Crinone® (progesterone gel) is a bioadhesive vaginal gel containing micronized progesterone in an emulsion system, which is contained in single use, polypropylene vaginal applicators. The carrier vehicle is an oil-in-water emulsion containing the water swellable, but insoluble polymer, polycarbophil. The progesterone is partially soluble in both the oil and water phase of the vehicle, with the majority of the progesterone existing as a suspension. Physically, Crinone has the appearance of a soft, white to off-white gel.

Replens is a hormone-free vaginal moisturizer. Ingredients include purified water, glycerin, mineral oil, polycarbophil, carbomer homopolymer type B, hydrogenated palm oil, glyceride, sorbic acid, and sodium hydroxide. This product will act as the placebo in this study.

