7.1.4 Treatment Compliance and Adherence

The Investigational Pharmacy will keep an Investigational Drug Accountability Record for the medication and placebo, which keeps track of study drug that is received, dispensed and returned. Subjects will be asked to maintain a diary documenting each drug application. Compliance with the treatment protocol will be assessed at each visit. The subject diary will be reviewed. Patients will be asked to return all unused medication packages. Unused study drug will be returned to the Investigational Pharmacy to count the remaining drug to assess compliance. Subjects will not be terminated from the study for non-compliance. However the compliance protocol will be considered in secondary analyses to determine if there is any difference in effect between compliers and non-compliers.

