5. *Binary Secondary Endpoints* will use an exact binomial confidence interval to estimate differences between groups and will be tested using Fisher's Exact test. The confidence level will be set at 90% and the Type I error at 10%. Binary outcomes include
 - a. Presence of WMI pre- and post-operatively
 - b. Completion of MRIs
 - c. Completion of Bayley III at 18 months
6. *Per Protocol and As Treated*
 - a. The analyses of the primary and secondary endpoints described above will be repeated with alternatives to the intention to treat cohort.
 - b. A 'strict' *per protocol* analysis will be used, considering only those subjects who were eligible for the study and who received the treatment as specified in the protocol. This analysis will consider only those subjects who completed at least 90% of their doses at the time of study-based discontinuation (pre-planned at XX weeks or due to earlier labor and delivery). Adherence will be measured in two ways (1) number of medication doses returned and (2) mother's diaries of medication use. Differences in the two measures of adherence will be described.
 - c. As a sensitivity analysis, a 'relaxed' *per protocol* analysis will follow (a) but use completion of 80% of doses instead of 90% of doses, as the cut-off.
 - d. An *as treated* analysis will consider subjects based on their 'dose of progesterone' based on their assignment to control or intervention arm, as well as adherence to study drug in the progesterone arm. In this case we will include dose as a continuous covariate in a regression model, using linear regression for continuous outcomes or logistic regression for binary outcomes. We will assess interactions between dose and treatment arm. This analysis will estimate the effect of the treatment intervention conditional on different levels of adherence to study medication.

7. *Modeling to Adjust for Covariate Imbalance.* Linear or logistic regression analyses of the primary and secondary outcomes will be carried out with adjustment for baseline covariates of fetal brain maturation and development. The covariates will include type of CHD (primary cardiac diagnosis), race, ethnicity, maternal education and socioeconomic status, presence of 22q11 deletions, other identified genetic anomalies and (*APOE*) genotype.
8. Missing data and truncation by death

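### SAP item 6d's dose-by-arm interaction is identical to dose and cannot be estimated, and neither model that remains gives the effect by adherence level that 6d promises

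*SAP*

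**What the plan says.** Item 6d of the SAP (Efficacy Analysis, Per Protocol and As Treated) classifies subjects by a dose of progesterone. That dose follows from the assigned arm, "as well as adherence to study drug in the progesterone arm". It enters as a continuous covariate in a linear model for continuous outcomes and a logistic model for binary ones. The item continues: "We will assess interactions between dose and treatment arm". It closes with its aim: "This analysis will estimate the effect of the treatment intervention conditional on different levels of adherence to study medication".

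Three other places bear on this:

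- Protocol 7.1 describes the control product: "Replens is a hormone-free vaginal moisturizer".
- Adherence is not recorded in one arm only. SAP 6b says "Adherence will be measured in two ways (1) number of medication doses returned", with diaries as the second measure. Protocol 7.1.4 says "Subjects will be asked to maintain a diary documenting each drug application" and "Unused study drug will be returned to the Investigational Pharmacy to count the remaining drug to assess compliance", and its accountability record covers placebo as well as active drug. SAP item 4f compares adherence between the arms.
- Protocol 7.1.4 wants compliance considered in secondary analyses "to determine if there is any difference in effect between compliers and non-compliers".

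**The concern.** An interaction between dose and arm can be estimated only if dose varies in both arms. As 6d defines it, dose varies in one arm and is constant at zero in the other, so the planned term carries no information beyond dose itself.

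The practical risk lies in what happens next. Software will drop the redundant column, and a dose slope will still be printed. Under 6d's closing sentence that slope could be reported as a treatment effect at different levels of adherence, which it is not. Item 6a applies these analyses to the primary and secondary endpoints, and the SAP's footnote on publications foresees a paper covering the primary endpoint together with adherence. The result could therefore appear beside the main finding.

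**Working it through.** Item 6d states no figure, so there is none to reproduce. The check is algebraic, followed by the precision of the alternative.

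**Inputs from the documents.** Dose is set by arm and by adherence in the progesterone arm (SAP 6d). The placebo contains no hormone (Protocol 7.1). There are 40 evaluable subjects per arm, the Bayley SD is 15 and confidence is 90% (Protocol 6.4). These inputs return the protocol's own half-width for the Motor Scale: 1.665 × 15 × √(2/40) = 5.58, printed as 5.6.

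**Assumed inputs.** The documents give no adherence distribution. I take an adherence SD of 5, 12 or 25 percentage points and, in step 3 only, a mean of 80%.

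**Step 1: the interaction.** Let A be arm (0 or 1) and h the proportion of doses taken. Then D = A × h, and A × D = A² × h = A × h = D for every subject. The same holds for dose in mg, since controls still have 0.

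| Model columns | Rank |
|---|---|
| 1, A, D, A×D | 3 of 4 |
| 1, D, A×D | 2 of 3 |
| 1, A, D | 3 of 3 |
| 1, D | 2 of 2 |
| 1, A, h, A×h (h in both arms) | 4 of 4 |

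Centring dose does not help (still 3 of 4). The duplication sits in the linear predictor, so it affects the logistic model equally.

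**Step 2: arm plus dose.** With A in the model and no other covariates, controls all sit at D = 0 and fix only the intercept. The slope estimate is the adherence slope within the progesterone arm. In one simulated data set of 40 per arm both were −1.2478. Controls do enter the pooled residual variance: in a simulated check, tripling the spread of control outcomes moved the slope's standard error from 20.1 to 43.8. The slope thus compares better with worse adherers in one arm, and that comparison is not randomised.

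**Step 3: dose alone.** This slope is a weighted average of the between-arm difference divided by mean adherence and the same within-arm slope. The weights are the sums of squares of D: between arms 40 × 0.80² / 2 = 12.8; within arms 39 × SD².

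| Adherence SD | Within-arm sum of squares | Weight on within-arm slope |
|---|---|---|
| 0.05 | 0.0975 | 0.0975 / 12.8975 = 0.8% |
| 0.12 | 0.5616 | 0.5616 / 13.3616 = 4.2% |
| 0.25 | 2.4375 | 2.4375 / 15.2375 = 16.0% |

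Dose alone is therefore mostly the arm difference rescaled, while arm plus dose is wholly the within-arm slope. The two answer different questions, and neither compares the arms at a given level of adherence.

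**Step 4: precision with adherence in both arms.** The arm-by-adherence coefficient is the difference of two within-arm slopes. Its 90% half-width per 10 percentage points is t × 15 × √(2/39) / SD × 0.1, with t = 1.665 (76 df). The numerator is 1.665 × 15 × 0.2265 × 0.1 = 0.566.

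- SD 0.05: 0.566 / 0.05 = 11.3 Bayley points
- SD 0.12: 0.566 / 0.12 = 4.7
- SD 0.25: 0.566 / 0.25 = 2.3

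**The case against.** The best defence is that an estimable reading exists. Item 6b speaks of doses for subjects in general, and 6d's last sentence speaks of adherence to study medication. If dose means study medication taken in either arm, the interaction can be fitted. But 6d itself defines the quantity as progesterone dose and counts adherence in the progesterone arm only. The two halves of the item conflict, and the text must say which governs.

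A second defence is that nothing printed would change, because fitted values are the same with or without the redundant column. That is true, and it keeps the point minor. It does not cure the mismatch between the slope that remains and the effect announced.

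Three stronger readings are tempting, and the documents do not support them:

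- *Only arm plus dose is left.* Item 6d's one explicit modelling instruction is to include dose as a covariate, so dose alone is equally open.
- *Controls contribute nothing.* They do not move the unadjusted slope, but they affect its standard error and p-value. Once covariates are added they can move the slope too.
- *The redundant term inflates false positives.* Any inflation would come from confounding between adherence and outcome. It would be there had the interaction sentence never been written, and its size depends on an adherence spread and an adherence-outcome correlation that neither document gives.

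**Conclusion.** The point holds as a minor one. Item 6d specifies a term that cannot be estimated in either model type, leaves open which of two different fits replaces it, and promises an effect by adherence level that neither fit delivers. The rank result rests on 6d's own definition and on a control dose of 0, which follows from the hormone-free placebo but is not printed; it does not depend on the adherence distribution.

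Items 6b and 6c restrict the cohort by adherence but do not contrast compliers with non-compliers, so they meet the aim in Protocol 7.1.4 only in part.

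A reader might infer that the trial's main result is in doubt. It is not: the primary t-test is by randomised arm, and the sample size and safety analysis do not use dose.

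**What to change.** Settle the wording of 6d before outcomes are analysed by arm.

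**If the effect by adherence is meant**, as the last sentence of 6d and Protocol 7.1.4 indicate: replace the dose-by-arm term with a model containing arm, adherence and arm by adherence. Define adherence as the proportion of assigned doses taken, in both arms, once by returned doses and once by diary. Label the analysis exploratory. State that adherence is observed after randomisation, and that the interaction is interpretable only if adherence relates to outcome similarly in the two arms.

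**If a progesterone-dose analysis is meant**: delete the interaction, state whether arm is in the model, reword the last sentence so that it no longer announces an effect by adherence level, and label this analysis exploratory as well.

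Either change is to SAP text only, since both adherence measures are already collected in both arms. The first option costs precision. At an adherence SD of 5 points, its half-width of 11.3 per 10 points of adherence is nearly twice the 6-point mean difference that Protocol 6.4 calls clinically relevant. It is also biased if the link between adherence and outcome differs by arm. The second option gives up the effect by adherence level.

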Table 1 shows that for the Bayley-III Motor Scale, assuming 40 evaluable subjects per treatment group, and an SD of 15, the $\frac{1}{2}$ width of a two-sided 90% confidence interval on the mean difference is expected to be 5.6. Thus, for example, if the mean difference is 6.0 units, a clinically relevant value for this population, the 90% two-sided confidence interval is expected to be on the order of (0.4, 11.6), suggesting that while only a minor effect cannot be ruled out, important positive effects of progesterone appear possible. In contrast, if there is no effect of progesterone we expect an interval centered around zero with i.e. (-5.6, 5.6). This initial study will thus provide important information about the magnitude of the effect of progesterone, and an indication of whether it is worthwhile to proceed with further trials. For TMS, results from [name] (personal communication) estimated the mean (median) value of TMS in a similar cohort to be 10.1 (10.0) with a standard deviation (SD) of 1.06 and range of 8.0 to 13.5. Conservatively assuming an SD that is 25% larger than that in the pilot data (SD=1.32), Table 1 shows that, with a sample size of 60 per group, two-sided 90% confidence intervals for the mean difference in TMS are anticipated to have a $\frac{1}{2}$ width on the order of ± 0.44 . Thus for TMS, if the mean difference is on the order of 2.0, the 90% confidence interval would be (1.56, 2.44). Estimated SD's for VMWM are not yet available.

Table 2: Expected endpoints of 90% confidence interval (CI) for different scenarios for PVL. Calculations are based on Pearson's Chi-square Method for n=60 (pre-surgical) or, conservatively) n=52 (post-surgical) per group.

Proportion in Control Group	Proportion in Treated Group	True Difference in Proportions	Expected Endpoints of 90% CI
Post-natal PVL (pre-surgical, n=60)			
19.0%	8.5%	10.5%	(0.3%, 20.7%)
19.0%	19.0%	0%	(-11.8%, 11.8%)
Post-operative increase in PVL from baseline (n=52)*			
38.0%	24.0%	14%	(-0.8%, 28.8%)
38.0%	38%	0%	(-14.6%, 14.6%) (-15.7%, 15.7%)
*Conservatively as we expect n=52 to 56 post-operatively			

Next we consider the categorical outcomes. In pilot data ([name], personal communication), 19% of subjects had some PVL prior to surgery and 38% of infants increased the level of

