PVL post-surgery. As part of our secondary aims, the pilot study is intended to estimate the differences in these outcomes between groups. To recruit 40 evaluable subjects at 18 months we anticipate having 60 patients available pre-surgery (post-natal) and 52 to 56 after surgery. Table 2 shows that if PVL at baseline is 19% in the control group, and the true effect is 10.5%, then the endpoints of the 90% CI are (0.3%, 20.7%) This would suggest that while we could not rule out essentially a null effect of progesterone, the evidence would suggest a possible substantial effect. In contrast if there were no effect we expect the confidence interval to be centered near zero with endpoints of $\pm 11.8\%$. Similarly, if the post-operative increase in PVL is 38% in the control group, and the true effect size is 14%, then the 90% confidence interval is expected to have endpoints of the 90% CI are (-0.7%, 28.7%). Again, while we could not rule out essentially a null effect of progesterone, the evidence would suggest a possible substantial effect. In contrast if there were no effect we expect the confidence interval to be centered near zero with endpoints of $\pm 15.7\%$.

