¹ We anticipate the trial resulting in at least two publications related to endpoints. In advance of seeing the unblinded data we anticipate a publication describing in depth results related to the primary endpoint and adherence. A brief description of key MRI-based endpoints may be included. A second publication will focus on MRI-based endpoints.

3. Impaired maternal-fetal environment (presence of 1 or more of gestational hypertension, preeclampsia, gestational DM, maternal tobacco use, maternal hypothyroidism)
4. Delivery Complications (abruption, post-partum bleeding, DVT/PE, perinatal mood/anxiety disorder, wound complications (infection, breakdown))
5. Postmenstrual age of neonate at time of birth,
 - a. Categorical: born earlier than 37 weeks postmenstrual age (PMA)
 - b. Continuous: PMA
6. Type of Delivery (Vaginal, Elective C-section, Emergent C-section)
7. Birthweight (BW), absolute and as Z-score
8. Placental descriptors: (placental weight (PW), PW < 10th percentile, ratio of BW to PW, presence of infarction, fetal vascular malperfusion, maternal vascular malperfusion, fetal vascular thrombi).
9. Brain growth and development. Trajectories of total and regional brain volumes and TMS from fetal to first post-natal MRI,
10. Post-operative seizures
11. Microhemorrhage and infarction
12. Age at post-operative MRI
13. Operative management variables (Cardiac operation during first admission y/n, age at first operation, cardiopulmonary bypass (CPB) y/n, weight at first operation, Clancy class, , deep hypothermia circulatory arrest (DHCA) time, Total support time (TST), antegrade cerebral perfusion time, need for extracorporeal membrane oxygenation (ECMO), additional operations with CPB, additional TST, additional DHCA)
14. Mortality (in-hospital, on-study and post-study)
15. Length of stay and selected complications for first surgical admission
16. Weight, length and HC at 18 months, absolute and as WHO percentile and Z-score

Intention to Treat Principle Unless otherwise specified, all analyses are conducted on an ‘as-randomized’ basis, irrespective of adherence to treatment. This analysis follows the intention to treat principle pre-specified in the protocol.

Descriptive Statistics (Intention to treat cohort)

1. Analyses will be done for the overall cohort as well as by primary cardiac diagnosis (HLHS, TGA, Other).

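### SAP Efficacy Analysis item 7 puts at least 10 logistic model terms on binary outcomes, one with only about 16 to 23 expected events, and has no safeguard for sparse data

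*SAP*

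**What the plan says.** SAP, Efficacy Analysis, item 7: "Linear or logistic regression analyses of the primary and secondary outcomes will be carried out with adjustment for baseline covariates". The list is fixed. APOE genotype is one of its eight members, and the other seven are named as follows: "The covariates will include type of CHD (primary cardiac diagnosis), race, ethnicity, maternal education and socioeconomic status, presence of 22q11 deletions, other identified genetic anomalies". CHD type has three groups, given in Descriptive Statistics item 1 as "primary cardiac diagnosis (HLHS, TGA, Other".

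Item 5 names the binary secondary endpoints. The first is "Presence of WMI pre- and post-operatively"; the others are completion of the MRIs and completion of the 18-month Bayley. Their main analysis is Fisher's exact test with an exact 90% interval and no covariates.

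Item 7 names no estimation method, so the default is ordinary maximum likelihood. It gives no coding for race, education or APOE, no minimum number of events, no rule for sparse levels, and no penalised or exact fallback. Protocol section 6.3.2 planned covariate modelling only for TMS, VMWM and the Bayley scales, all continuous. The extension to binary outcomes comes with the SAP.

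Protocol section 6.4 gives the planning rates: "19% of subjects had some PVL prior to surgery and 38% of infants increased the level of" PVL after surgery. Table 2 there assumes 60 per group before surgery and 52 after.

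**The concern.** In maximum-likelihood logistic regression, the count of the rarer outcome limits how many terms the model can carry. With one or two events per term, coefficients drift away from zero, and a covariate level with few subjects may have no finite estimate.

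Two things are at stake. The adjusted odds ratio for white matter injury would stand beside the Fisher result and look stronger than the data support; reducing white matter injury is a named secondary aim, and the SAP expects a second publication on the MRI endpoints. Also, if a coefficient cannot be estimated, the analyst must decide which terms to drop with the data in hand, because the SAP sets no rule.

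**Working it through.** **1. The protocol's own figure.** Table 2 gives a 90% interval of (0.3%, 20.7%) for 19% vs 8.5% at n = 60 per group. The unpooled interval is d ± 1.645 × √(p₁q₁/n + p₂q₂/n).
- 0.105 ± 1.645 × √(0.19 × 0.81/60 + 0.085 × 0.915/60) = 0.105 ± 0.102, or (0.3%, 20.7%). This reproduces the table and confirms the inputs.

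**2. Model terms.** CHD type takes 2 terms. The other seven adjusters (race, ethnicity, maternal education, SES, 22q11, other genetic anomaly, APOE) take at least 1 each. That makes at least 9, or 10 with arm. If race, education and APOE each have three levels, it is 12, or 13 with arm.

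**3. Events, n × (p₁ + p₂), or the count implied by attrition.**

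| Outcome | Expected events | Per term (10 terms) |
|---|---|---|
| Pre-operative PVL, planned effect | 60 × (0.19 + 0.085) = 16.5 | 1.65 |
| Pre-operative PVL, no effect | 120 × 0.19 = 22.8 | 2.3 |
| Post-operative PVL increase, planned effect | 52 × (0.38 + 0.24) = 32.2 | 3.2 |
| Post-operative PVL increase, no effect | 104 × 0.38 = 39.5 | 4.0 |
| Post-operative MRI missing | 2 × (60 − 56) to 2 × (60 − 52) = 8 to 16 | 0.8 to 1.6 |
| Bayley not completed | 110 × 0.24 to 130 × 0.24 = 26 to 31 from 5% then 20% attrition (1 − 0.95 × 0.80 = 0.24); 30 to 50 from 110–130 enrolled less 80 evaluable | 2.6 to 5 |

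With 13 terms the pre-operative ratio under the planned effect is 16.5/13 = 1.27.

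**4. True treatment effects.**
- Pre-operative: ln(0.085/0.915) − ln(0.19/0.81) = −0.93 (OR 0.40).
- Post-operative: ln(0.24/0.76) − ln(0.38/0.62) = −0.66.

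**5. Simulation.** Trials were generated at these rates and fitted with the item 7 list. The documents give no covariate frequencies. Assumed values: CHD 30/30/40%; race 20% (range 10–30%, or four levels); ethnicity 5–10%; education two or four levels; continuous SES; 22q11 2–10%; other anomaly 10–25%; APOE one or two terms.

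- *Pre-operative, planned effect.* The mean or median adjusted arm log OR was about −1.05 to −1.18. Since 1.05/0.93 = 1.13 and 1.18/0.93 = 1.27, it is about 13–28% too large, an OR of about 0.31–0.35 against 0.40. The unadjusted mean was mostly −0.95 to −0.98, already 3–6% too large (highest −1.00).
- *Post-operative, planned effect.* Typically 12–17% too large (for example −0.75 to −0.77 against −0.66). Over all codings tried the range was −0.73 to −0.83, or 10–25%; the top comes from 15 terms including arm.
- *No effect.* The mean was near zero. The nominal 10% likelihood-ratio test rejected in about 11–13% of trials. The 10% Wald test rejected the true value in 9–12%, over scenarios with and without an effect.
- *Firth penalty, full list.* −0.88 to −0.92 pre-operatively and −0.65 to −0.66 post-operatively.
- *Firth penalty, arm plus CHD stratum.* −0.89 to −0.95 and −0.65 to −0.66.

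**6. Fits in which some coefficient has no finite estimate**, by assumed 22q11 prevalence:

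| Outcome | 2% | 5% | 10% |
|---|---|---|---|
| Pre-operative, planned effect | 80% | 64% | 42% |
| Pre-operative, no effect | 67% | 43% | 20% |
| Post-operative, planned effect | 54% | 26% | 8% |
| Post-operative, no effect | 48% | 18% | 3% |

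At 4%, pre-operative values of 64–74% (planned effect) and 46–56% (no effect) were found. Without the 22q11 term, the planned-effect figures fall to 32% pre-operatively and 5% post-operatively. The arm coefficient itself was non-finite in at most 1% of fits.

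**The case against.** The best defence is that item 7 is supplementary. Item 5 keeps the unadjusted Fisher's exact test as the main binary analysis, the primary endpoint is a continuous score compared by a t-test, and the trial is exploratory with a 10% error rate. All of that stands, and it limits the point to a secondary, adjusted result. It does not make the adjusted odds ratio sound where it is reported.

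A reader might infer more than the documents support:

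- *That every binary outcome has about 16 events.* That figure belongs to pre-operative PVL under the planned effect. Missing MRIs are about as few or fewer; post-operative increase and Bayley non-completion have more.
- *That most fits separate and that this exaggerates the treatment odds ratio.* The frequency depends on a 22q11 prevalence that the documents do not give. The coefficient that diverges is a nuisance term. In one run the mean arm log OR was −1.13 in separated fits and −1.12 in the others, so separation does not cause the bias.
- *That the adjusted odds ratio will set the size of the multi-centre trial.* Protocol section 6.4 ties that purpose to the Motor Scale mean difference and plans PVL in terms of differences in proportions.
- *That the covariate list must be cut for all binary outcomes.* The Firth penalty removes the upward bias with the full list kept.

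**Conclusion.** The concern holds in limited form. Item 7 carries too many terms for pre-operative white matter injury and for MRI completion, and lacks a sparse-data rule for any binary outcome. When a true effect exists, the adjusted log odds ratio is too large by roughly 13–28% pre-operatively and 12–17% post-operatively, and part of the pre-operative excess (3–6%) is present without adjustment. With no effect there is no bias in the estimate and only slight test inflation.

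Separately, a sparse nuisance coefficient has no finite estimate in about 40–75% of pre-operative fits under the planned effect and 20–55% with no effect, as the assumed 22q11 prevalence falls from 10% to 4%. This is a problem of unplanned model choice and does not drive the treatment bias.

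The event counts follow from the protocol, taking PVL as the SAP's white matter injury. The post-operative figures use the rate of PVL increase as a stand-in for presence of injury, whose rate is not given. The MRI count considers only the post-operative scan. Bias and separation figures rest on the assumed covariate frequencies and on the coding, which the SAP leaves open. Primary inference is unaffected.

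**What to change.** In item 7, state that binary outcomes will be fitted by Firth-penalised logistic regression with profile-penalised 90% confidence intervals. For these models, combine 22q11 deletion and other genetic anomalies into one term. This fits Descriptive Statistics item 6, which already classes 22q11 deletions as Abnormal; the SAP should say where its Suspect class falls. State the coding of race, education and APOE.

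For outcomes with few events (pre-operative white matter injury, MRI completion), also report either a model with arm and CHD stratum only, or a Mantel-Haenszel risk difference stratified by CHD group with a 90% interval. The linear models for continuous outcomes need no change.

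The cost is a few sentences in the SAP, a little extra analysis, and an adjusted odds ratio that will look slightly less favourable. With the full list, the penalised pre-operative estimate averaged −0.88 to −0.92 against a true −0.93, so any remaining error is small and towards no effect.
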